6.7. Early Termination Procedures

The term "Early Termination" refers to a participant's non-completion of the study. Should a participant decide to withdraw, all efforts will be made to complete and report observations as thoroughly as possible. In the event that a participant is withdrawn from the study, the reason for the withdrawal and the party who initiated the withdrawal (participant or Clinical Investigator) will be documented. Should the participant decide to withdraw, documentation of the early termination will be made and an attempt to conduct an early termination visit (which will occur at week 16 and include the clinic visit procedures for Visit 7).

The primary reason for a participant withdrawing prematurely should be selected fiom the following standard categories:

Adverse Event- event which results in discontinuation of the study food by the participant or that in the judgment of the Clinical Investigator for the best interest of the participant requires discontinuation of study food (includes all categories of study food relatedness; Not Related, Unlikely, Possibly, Probably, and Definitely).

Death -death of the participant.

Withdrawal of Consent- participant desires to withdraw from further participation in the study in the absence of a medical need to withdraw determined by the Clinical Investigator.

Lost to Follow-Up- participant did not return for one or more follow-up visit(s) following dispensing of test product and could not be contacted thereafter. The reason for withdrawal was unknown and could not be documented.

Other- causes of premature termination from the study other than the above, such as theft or loss of study foods, pregnancy, termination of study by Sponsor, etc.

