9.2.2. Relationship

The Clinical Investigator will also judge the likelihood that the AE was related to the diet plan administered and document this on the appropriate eCRF as:

Jason Pharmaceuticals, Inc. BI0-1607 (MED 019) 21 .June 2016; Version 1.7 Confidential

NOT RELATED	This category applies to those adverse experiences which, after careful consideration, are clearly and incontrovertibly due to extraneous causes (disease, environment, etc.).
UNLIKELY	In general, this category can be considered applicable to those experiences that after careful medical consideration at the time they are evaluated, arc judged to be, unlikely related to the study foods administered.
POSSIBLY	This category applies to those adverse experiences for which, after careful medical consideration at the time they are evaluated, a connection with the study foods administration appears possible but cannot be ruled out with certainty.
PROBABLY	This category applies to those adverse experiences that, after careful medical consideration at the time they are evaluated, are felt with a high degree of certainty to be related to the study foods.
DEFINITELY	This category applies to those adverse experiences which, the Clinical Investigator feels are incontrovertibly related to the study foods.

Appropriate therapeutic action and follow-up measures will be performed by the Clinical Investigator in accordance with good medical practice.

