#### **11.0. SAFETY ANALYSIS**

Safety assessments will be determined from intervention-emergent AEs that occur after randomization at Visit 2 (week 0). Possible differences in the number of participants with at least one AE will be assessed with Chi-Square or Fisher's exact test.

Participants who achieve a BMI of  $19.0 \text{ kg/m}^2$  or below will discontinue the weight loss diet and begin a maintenance diet and will be asked to return for remaining clinic visits. These participants will be noted in the safety analysis.

Vitals (blood pressure, pulse rate) will be summarized by group with descriptive statistics.

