
Table 4.10  
Secondary Outcome Variable: Weight Loss Program Adherence Descriptive Statistics and P-values

Parameter		TSFL	MEDD
Meal Replacement^	Mean (SEM)	Mean (SEM)	Mean (SEM)
	Median	Median	Median
	Q1, Q3	Q1, Q3	Q1, Q3
	Min, Max	Min, Max	Min, Max
	Corr (p-value)+	0.xxx (x.xxx)	0.xxx (x.xxx)
Nutrition Support Contact	Mean (SEM)	Mean (SEM)	Mean (SEM)
	Median	Median	Median
	Q1, Q3	Q1, Q3	Q1, Q3
	Min, Max	Min, Max	Min, Max
Coaching Contact	Mean (SEM)	Mean (SEM)	
	Median	Median	
	Q1, Q3	Q1, Q3	
	Min, Max	Min, Max	
	Corr (p-value)+	0.xxx (x.xxx)	

^average meal replacement (per day) across the 16-weeks of the study

+spearman's rank-order correlation between the corresponding parameter and absolute change in body weight from baseline (Visit 2; week 0) to end of study (Visit 7; week 16)

Table 4.11  
Secondary Outcome Variable: Nutrition Support Contact P-values

Group	Parameter	Initial & Discretionary NS contact*		Initial NS contact or None**	p-value^
MEDD	% weight loss >= 5%	N (%)	N (%)	N (%)	x.xxx
TSFL	% weight loss >= 5%	N (%)	N (%)	N (%)	x.xxx

^p-values shown are generated from Fisher's exact test

\*at least two NS contacts for MEDD or at least one NS contact for TSFL

\*\*at most one NS contact for MEDD or none for TSFL

Table 5  
Summary of Subjects with at Least One Intervention-emergent Adverse Events

	Control	TSFL	MEDD	Intervention p-value*
Any Adverse Event	N (%)	N (%)	N (%)	x.xxx
Serious	N (%)	N (%)	N (%)	x.xxx
Severe	N (%)	N (%)	N (%)	x.xxx
Related to Study Treatment*	N (%)	N (%)	N (%)	x.xxx

\*p-values shown are generated from Chi-Square or Fisher's exact test, as appropriate

\* Probably or Definitely Related to Study Treatment.

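### SAP Table 5's only relatedness row leaves out participants whose highest grade is Possibly, so it understates adverse events attributed to the diet programs

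*SAP*

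**What the plan says.** Protocol 9.2.2 makes relatedness a recorded judgement on every AE: "The Clinical Investigator will also judge the likelihood that the AE was related to the diet plan administered". The scale has five grades, and Protocol 6.7 repeats them when it describes withdrawal for an AE ("includes all categories of study food relatedness; Not Related, Unlikely, Possibly, Probably, and Definitely"). Possibly applies when "a connection with the study foods administration appears possible but cannot be ruled out with certainty". Probably is kept for events that "are felt with a high degree of certainty to be related to the study foods", and Definitely for events whose link is beyond dispute.

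The safety text in Protocol 8.2.3 and SAP 11.0 specifies one between-group AE comparison: "Possible differences in the number of participants with at least one AE will be assessed with Chi-Square or Fisher's exact test". Neither section says which grades count as related.

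That choice is made only in SAP 17.0. Table 5, titled "Summary of Subjects with at Least One Intervention-emergent Adverse Events", has four rows: any AE, serious, severe, and "Related to Study Treatment". A footnote restricts the last row to "Probably or Definitely Related to Study Treatment". The shell gives each row a p-value. SAP 16.0 lists Table 5 as the only AE table, produced for the modified ITT population. No table or listing by relatedness grade is planned.

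**The concern.** The protocol separates events for which a link appears possible from those for which it is judged unlikely or absent. Table 5 does not carry that separation through. A participant whose highest grade is Possibly falls outside the related row, just like one graded Unlikely or Not Related. No other planned output shows the Possibly group, so a reader of the report could not recover it.

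Protocol section 3 presents the trial as evidence for commercial programs that should have published support for both safety and efficacy. How many participants had an AE that the investigator thought might be due to the program is an obvious safety question. The planned row answers a narrower one: how many had an AE that the investigator was nearly sure was due to it.

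**Working it through.** No figure in the plan needs reproducing, because the documents state no AE rate or relatedness rate. The check is a comparison of texts, followed by an illustration on assumed rates.

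**Step 1. Follow each grade into Table 5.** The table counts participants, so what matters is a participant's highest grade.

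| Highest grade | Sense in Protocol 9.2.2 | In the related row? |
|---|---|---|
| Not Related | clearly due to other causes | no |
| Unlikely | link judged unlikely | no |
| Possibly | link appears possible | no |
| Probably | high degree of certainty | yes |
| Definitely | beyond dispute | yes |

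Three grades do not judge the link unlikely or absent. The row counts two of them and drops the least certain.

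**Step 2. See where the dropped participant still appears.** He or she counts under any AE, and under serious or severe if an event qualifies. If an AE led to withdrawal, he or she also appears in the AE discontinuation line of SAP Table 1, which covers every relatedness grade under Protocol 6.7. A participant with both a Possibly and a Probably event stays in the related row.

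**Step 3. Direction.** Let a be the proportion of an arm with at least one Probably or Definitely related AE, and b the further proportion whose highest grade is Possibly. The planned row shows n × a. A row that includes Possibly shows n × (a + b). Because b cannot be negative, the cut can only lower the count or leave it unchanged. The omitted share is b / (a + b), whatever n is.

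**Step 4. Illustration.** Take n = 66, the number randomized per group in Protocol 8.1. The modified ITT denominator may be smaller. Assume a of 2% to 5% and b of 3% to 20%; neither range comes from the documents.

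| a | b | Planned row, 66 × a | With Possibly, 66 × (a + b) | Omitted share, b / (a + b) |
|---|---|---|---|---|
| 2% | 3% | 1.3 | 3.3 | 0.03 / 0.05 = 60% |
| 2% | 20% | 1.3 | 14.5 | 0.20 / 0.22 = 91% |
| 5% | 3% | 3.3 | 5.3 | 0.03 / 0.08 = 38% |
| 5% | 20% | 3.3 | 16.5 | 0.20 / 0.25 = 80% |

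The spread shows how far the answer depends on rates that the plan does not give.

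**Step 5. Does the p-value on the row mean anything?** The definitions from Unlikely to Definitely are worded in terms of study foods. Under the flow-chart footnotes in Protocol 6.2 and the program descriptions in 6.4.1, Control gets ordering instructions for study food only at week 16, after all visits are complete. The sentence introducing the scale speaks of the diet plan, which would fit Control, but the grade definitions do not. A between-arm test of this row therefore compares a judgement that is not defined in the same way in every arm. Adding Possibly does not cure that.

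**The case against.** The strongest defence is that nothing is hidden or contradicted. The protocol never says which grades count as related, so the footnote breaks no rule. The cut is prespecified, because the shells are part of the SAP; it is printed under the table; and it applies alike to all arms. Possibly events stay in the any-AE row, and the prespecified comparison ignores relatedness. All of this stands, and it limits the point to one attribution row. It does not explain why that row should be the only view of relatedness, or why a grade the protocol takes care to define should appear nowhere.

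A second objection is that testing a wider related row would only test a weaker attribution with wording that does not fit Control. This also stands, and is why the fix asks for descriptive rows or a caveated p-value.

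A reader might be tempted to go further in four ways that the documents do not support:

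- That every Possibly event vanishes. Table 5 counts participants, so an assumed share of events cannot simply be subtracted from the participant count.
- That the row will be nearly empty. No AE rates are given.
- That the cut favours the programs in the between-arm comparison. It is the same for all arms, and its effect on the contrast depends on unknown grade distributions.
- That the sponsor runs the safety summary. SAP 4.0 gives the analysis to Biofortis personnel, Protocol 9.2.4 treats that organisation as distinct from the sponsor, and the Clinical Investigator assigns the grades.

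**Conclusion.** The point holds as a limited one. Table 5 leaves participants whose highest grade is Possibly out of the only relatedness count, and neither Protocol 8.2.3 nor SAP 11.0 gives a reason. Relative to a definition that includes Possibly, diet-attributed AEs are understated. The direction is certain: the count is lower, or equal if nobody has Possibly as the highest grade. The size is not known, and the 38% to 91% range rests wholly on assumed rates. Total AEs, the any-AE comparison, the primary outcome and the sample size are untouched. The change is worth making because it alters a reported safety result and needs no new data.

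**What to change.** In SAP 11.0, define a related AE as one graded Possibly, Probably or Definitely. In Table 5, report by arm the number and percentage of participants with at least one such AE, and keep Probably or Definitely as a second row. Present both relatedness rows without p-values, or attach a note that the grade definitions refer to study foods that Control does not receive during the 16 weeks. Give the p-value footnote and the relatedness footnote different symbols, since the shell now uses an asterisk for both.

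The cost is a sentence in SAP 11.0, one extra table row and revised footnotes. The grades are already recorded on the eCRF, so no data collection changes and no information is lost. The downside for the sponsor is that the displayed related-AE percentages may be less favourable.
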